#### 2.4 Recruitment Strategy

#### 2.4.1 Description of Centers and Available Patient Pool

The target sample size for this trial is 90 patients, of whom 50% will be randomized to nocturnal home six times per week hemodialysis. Patients will be recruited from designated Clinical Centers in the United States and Canada (See Figure 2), which have a combined pool of more than 11,000 prevalent dialysis patients. Each Clinical Center will have the capacity to recruit a minimum of 20 patients into the trial. Data from the Lynchburg and Saratoga Springs nocturnal home hemodialysis programs suggest that between 5 to 10% of patients within their dialysis units have been trained and started on nocturnal home hemodialysis. Other programs have noted that a similar percentage of patients have initiated nocturnal home hemodialysis. [Piccoli, 2002]

Several programs in our consortium have accepted patients from outside of their own dialysis units for home hemodialysis training purposes. In Saratoga Springs, NY, patients travel from as far as 300 miles away for training and for the monthly follow-ups required of home training patients. This situation is similar to that described in Iowa City, IA, where home hemodialysis patients travel up to 300 to 400 miles for training and for monthly follow-up.

Each of the Clinical Centers in this consortium has contacted adjacent nephrology programs and dialysis units and has obtained permission to recruit patients from these units for a study in home nocturnal dialysis. Based on information provided from the Clinical Centers and the adjoining dialysis units, we have provided below in Table 2 a summary of the number of patients that will be available for recruitment into the nocturnal study from this clinical trials consortium.

Clinical Center	Number	Blacks	Whites	Males	Females	Other*	Total
Lynchburg, VA	336	210	126	184	152	400	736
Saratoga Springs, NY	333	27	296	173	160	1020	1353
New York City, NY (Rogosin Inst.)	565	245	149	283	282	600	1165
St. Louis, MO (Washington U)	683	499	118	311	372	730	1413
Kansas City, MO	367	145	220	194	183	400	767
Winston-Salem, NC (Wake Forest)	1169	625	517	596	575	650	1819
London, Ontario, Canada	566	17	515	300	266	0	566
Indianapolis, IN (Indiana U)	441	309	128	216	225	30	741
Iowa City, IA (U of Iowa)	186	10	166	93	93	680	866
U of Toronto -Toronto General Hospital	445	50	185	267	178	180	625
Humber River Regional Hospital	303	77	151	161	124	0	303

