A lower extremity performance battery (LEP) designed for use in a large epidemiological study, the Established Populations for Epidemiological Study of the Elderly (EPESE) is the measurement of choice for this study [Guralnik, 1994]. The LEP consists of 3 tasks that represent activities necessary to be mobile: standing balance, walking speed, and timed chair stands. The LEP combines gait speed, chair rise time, and balance skills into a cumulative score of function. The LEP score shows excellent reliability [Ostir 2002] and it is also highly responsive to change [Onder, 2002]. The tests discriminated risk of death and nursing home placement in the total older population in the EPESE study [Guralnik, 1994]. In a subset of older adults with no self-reported disability reported from EPESE studies, the LEP also predicted functional decline and hospitalization over 4 years. Recently, the LEP was used in a clinical setting as a quantitative estimate of future risk for hospitalization and decline in health and function in a population of older adults [Studenski, 2003]. In that clinical setting, the physical performance measures were independent predictors of use, change in health status, and decline in function in a primary care

clinical environment, after accounting for baseline status, age, a hospital risk estimator, and primary physician's risk estimate. Performance measures alone, or in combination with self-report measures also predicted outcomes better than self-report alone [Studenski, 2003].

Performance testing will be conducted prior to a dialysis treatment since performance scores on the LEP can be affected after a single dialysis treatment [Tawney, 2004]. Performance scores will be derived for each test (balance, walk, and chair stands); with a score of 0 representing the inability to complete the test and 4 the highest level of performance. Ordinal categories for the 4 meter walk, chair stands, and balance tests will assigned based on reference tables developed for elderly people who participated in the EPESE study [Guralnik, 1994]. The individual balance, walk, and chair stands scores category scores will also be summed to create am overall LEP (0 –12). The LEP incorporates missing data into the tests results by assigning a 0 score while those who are able to complete the test are assigned a score according to the quartile of performance. This means that patients who were not capable of performing a test were still assigned a score.

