# 6.2.7 Objective Tests of Physical Function

The Lower Extremity Battery (LEP: timed 4-meter walk, timed chair stand, and balance test) will be performed at baseline, 4 months and 12 months (Table 11 A). This test will be conducted by the study coordinator before the HD session since performance scores can be affected after a single HD treatment [Tawney, 2004]. The study coordinators will be trained by an experienced person familiar with the methods of this test prior to study start.

For the LEP, performance scores will be derived for each test with a score of 0 assigned to those unable to complete the test, and 4 indicating the highest level of performance. Ordinal categories for the 4-meter walk, chair stand, and balance test will be assigned based on reference tables developed for elderly people who participated in the EPESE study [Guralnik, 1994]. In addition, the individual scores for each of the 3 tests will be summed to create an overall LEP score (0-12). The LEP score incorporates missing data into the test results by assigning a score of 0 for missing values and for those unable to complete the test, while those who are able to complete the test are assigned a score according to a quartile of performance.

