As described in Section 9.3, the PHC/Mortality and LV mass/Mortality composites are the coprimary endpoints for evaluation of patient benefit in the trial. In addition, as described in Section 5.1.2, main secondary outcomes have also been designated for each of seven specific and conceptually distinct physiological or quality of life-related outcome domains. These include: i) change over 12 months in the PHC; and, ii) change over 12 months in LV mass (without the mortality components), which represent the main secondary outcomes for evaluation of the physical function and cardiac structure and function domains, respectively. The remaining outcome domains and associated main secondary outcomes are iii) depression/disease burden (change over 12 months in Beck Depression Inventory), iv) nutrition (change over 12 months in serum albumin), v) cognitive function (change over 12 months in the Trails B), vi) mineral metabolism (change over 12 months in average pre-dialysis phosphorus), and vii) clinical events (rate of non-access hospitalizations or death). The primary evaluation of the effects of the treatment interventions on each of these seven outcome domains will be based on the designated main secondary endpoints. Analyses of other outcomes within each domain will be regarded as exploratory. Hypertension and anemia are also stipulated as main outcome domains, but are not conducive to the designation of a single main endpoint.

Two-sided tests will be used when testing the effects of the interventions on both the primary and secondary endpoints. The primary and main secondary analyses will be conducted by intention-to-treat in the sense that all patients analyzed according to their randomized assignment, irrespective of whether they adhered to the interventions. As noted above, however, follow-up will be censored at the time of renal transplantation. The analyses of the main secondary endpoints will be tested at the 0.05 level, without formal adjustment for multiple comparisons. However, nominally significant effects on individual secondary outcomes will be interpreted as consistent with Type I errors unless accompanied by significant effects of the interventions on the primary outcomes and a consistent pattern of treatment effects across multiple secondary outcomes.

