# 9.11 Statistical Power

Estimates of parameters for determination of study power were obtained primarily based on information from the HEMO Study database, with downward adjustments in mortality and hospitalization rates to account for the expectation of lower comorbidity among patients eligible for nocturnal dialysis. During the first year of follow-up in the HEMO Study, the mortality rate was 12%/year, the transplant rate was 4%/year, the rate of all non-access hospitalizations was 1.19 per year, and approximately 80% of patients remained in active follow-up at the 12 month assessment. To assure the power calculations are conservative, we have projected that mortality and hospitalization rates will be 40% lower in the control group of this trial than in the HEMO Study, and that transplantation rates will be slightly higher (6% per year instead of 4%), reflecting the expectation of a younger average age and inclusion of more incident patients. Data from the HEMO Study was also used to estimate the standard deviation of the change in the PHC, average serum albumin, average serum phosphorus, average pre-dialysis systolic blood pressure after controlling for the baseline value of outcome and pre-specified covariates. The standard deviation estimate of 24 g for the change in LV mass was estimated from the standard deviation of the change in LV mass by MRI obtained in 153 patients over 9 months by Pitt et al (2003).

The minimum detectable effect sizes for the co-primary PHC/Mortality and LV mass/Mortality composite endpoints of were estimated under the following assumptions: a) the target sample size of 90 randomized patients is achieved, b) exponentially distributed survival, with a 7%/yr mortality rate in the control group, c) exponentially distributed transplantation, with a 6%/yr transplantation rate in both treatment groups, d) measurements at 12 months of the PHC and LV mass outcomes will be obtained in 80% of randomized patients, e) normally distributed changes in the PHC and LV mass in those patients with 12-month measurements, with standard deviations (without covariate adjustment) of 9.12 PHC units and 24.0 g, respectively, f) utilization of the log rank test as described in Section 9.3, without covariate adjustment, and g) use of Hochberg's procedure to maintain an overall Type I error rate of  $\leq 5\%$ .

FHN Nocturnal Protocol Version 3.3: October 15, 2008

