Estimated Detectable Effect Sizes for 80% or 90% Power for the Primary Outcomes

 As described in the text, under the Hochberg procedure the statistical power for each of the two primary outcomes depends in part on the effect size for the other outcome. Thus, the minimum detectable effect on the LV mass-Mortality composite is evaluated assuming treatment effects on the change in the PHC of either 0, 2.28 (corresponding to 25% of the estimated standard deviation of the change in the PHC score after covariate adjustment), or 4.56 units (corresponding to 50% of one standard deviation). Similarly, the treatment effects on the PHC-Mortality composite are evaluated assuming effects of either 0, 6 (25% of 1 SD) or 12 g on the

change in LV mass. The simulation results indicate the above calculations are accurate if the correlation between the change in LV mass and the change in the PHC score is between 0 and +0.5.

Table 15 provides the estimated minimum detectable effect sizes for each of the quantitative main secondary outcomes under the following assumptions: a) measurements obtained at 12 months in 80% of patients for each outcome, b) the standard deviations of the changes in each outcome (with covariate adjustment) are as indicated in Table 15, c) two-sided significance levels of 0.05 are applied to each outcome, without adjustment for multiple tests, d) utilization of the parametric analysis of changes with covariate adjustment outlined in Section 9.5. The power calculations do not take into account information provided by the 4 month measurements for patients with missing data at 12 months; thus, in this respect the values are slightly conservative. As in Table 14, the minimum detectable effects are provided both overall (without parentheses), and among the assumed 95% of patients who complete the post-randomization component of the nocturnal training program (with parentheses), assuming no treatment effect among those not successfully completing the training program.

#### Table 15

Estimated Detectable Effect Sizes for 80% or 90% Power for the Main Secondary Outcomes

Outcome Variable	Assumed SD of 1 Yr Change	80% power	90% power
PHC (points)	8.310	5.54 (5.83)	6.40 (6.74)
LV mass (g)	24.00	16.0 (16.8)	18.5 (19.5)
Average Albumin (g/dL)	0.296	0.198 (0. 208)	0.229 (0.241)
Average serum phosphorus (mg/dL)	1.636	1.08 (1.14)	1.26 (1.33)
Beck Depression Inventory (1 SD) 	-	0.67 (0.71)	0.77 (0.81)

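### Section 6.2.7 scores a missing lower-extremity test as 0, the worst value, so absence unrelated to function is counted as total loss of function

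*Protocol*

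**What the plan says.** Two sections describe how the LEP is scored. Each of three tests (balance, walk, chair stands) scores 0 to 4, and the three scores are summed to 0 to 12.

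- Section 6.2.7 starts by reserving 0 for patients unable to complete a test. It then says the score absorbs missing data "by assigning a score of 0 for missing values and for those unable to complete the test". Missing values and inability are named as two groups, both get 0, and no exception is made for the reason a value is absent.
- Section 5.1.5.2.1 says: "The LEP incorporates missing data into the tests results by assigning a 0 score". Its explanation is narrower: "This means that patients who were not capable of performing a test were still assigned a score".

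Section 9.9 treats unobserved 12-month responses as missing. They are to be handled by restricted maximum likelihood using baseline and month-4 data, with pattern-mixture sensitivity analyses.

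The LEP is a secondary outcome but not the priority outcome of its domain. On such outcomes Section 9.4 says: "Analyses of other outcomes within each domain will be regarded as exploratory".

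**The concern.** A score of 0 is sensible for a patient who is physically unable to do the test. It is not sensible for a patient who was simply not tested, and the protocol gives several routes to that state:

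- Follow-up ends at transplant or a switch to peritoneal dialysis (Section 3.2). Transplantation is assumed at 6% per year (Section 9.11).
- For patients who relocate, Sections 3.2 and 7.4 seek vital status, the co-primary outcomes and the central questionnaires. The LEP is not on that list.
- The LEP needs a coordinator in person, before dialysis and mid-week (Section 6.2.7, Table 9), whereas the SF-36 is done by telephone. Section 2.4.1 describes home patients travelling 300 to 400 miles to a center.

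What is at stake is the objective check on physical function. Section 5.1.5.2.1 calls objective measures vital because a self-reported outcome in an unblinded trial may be biased. Once absences have been filled with 0, the Section 9.9 methods have nothing left to act on.

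**Working it through.** **Plan figures.** The protocol states no mean, SD, power or completeness for the LEP, so there is no LEP figure to reproduce. The nearest inputs are the target ("The target sample size for this trial is 90 patients", so 45 per arm) and the 12-month completeness assumed for the main secondary outcomes ("measurements obtained at 12 months in 80% of patients for each outcome", so 0.80 × 45 = 36 per arm). These reproduce Table 15. At 80% power the detectable effect is (1.960 + 0.842) × SD × √(2/36):

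- PHC, SD 8.310: 5.49 (5.56 with the t distribution), against 5.54 stated.
- LV mass, SD 24: 15.8 (16.1), against 16.0 stated.

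The 80% figure is therefore a working assumption of the plan, but for other outcomes.

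**Effect of filling with 0.** Let μ be the mean LEP, σ its SD, and m the share missing for reasons unrelated to function. The expected mean in an arm becomes (1 − m)μ. It follows that:

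- With no treatment effect, the false difference (nocturnal minus control) is −(m_N − m_C) × μ.
- With equal m and a true effect δ, the expected difference is (1 − m)δ.
- The variance of the 12-month score becomes (1 − m)σ² + m(1 − m)μ².

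**Numbers (μ, σ and the missing shares are assumptions).**

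- A gap of 0.10 with μ = 6, 8, 10 gives a false difference of 0.6, 0.8, 1.0 points.
- With m = 0.20, μ = 8 and σ = 3, the variance is 0.8 × 9 + 0.16 × 64 = 17.4, so the SD rises from 3 to 4.2.

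**Simulation.** Settings: 45 per arm, values missing completely at random, analysis of covariance on baseline, baseline correlation 0.7, scores rounded and capped at 0 and 12, two-sided 0.05, 4000 runs. No true effect:

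| Missing, nocturnal / control | False difference (mean 8, SD 3) | Type I error | False difference (mean 10, SD 2) | Type I error |
|---|---|---|---|---|
| 20% / 20% | 0.0 | 5.2% | 0.0 | 4.7% |
| 22.5% / 17.5% | −0.40 | 8.1% | −0.47 | 8.0% |
| 25% / 15% | −0.78 | 16.2% | −0.98 | 20.2% |
| 30% / 10% | −1.56 | 51.8% | −1.95 | 62.8% |

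When the absent values are left missing, the bias stays within ±0.01 points and type I error is 4.5% to 5.8% for every split.

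With equal 20% missingness and a true shift of 1.5 points before capping, the estimate falls from 1.31 to 1.05 (mean 8) or from 1.14 to 0.90 (mean 10), a loss of one fifth. Power falls from 79.5% to 24.2%, or from 97.8% to 16.9%.

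**The case against.** The best reply is that only inability was meant. Section 5.1.5.2.1 explains the rule in those terms and expects many patients to be unable to do the tasks. Both sections contrast the 0 with the scores of patients who can complete a test. On that reading the rule scores components within a battery that was actually given, Section 9.9 covers absent visits, and the two coexist. This is a fair account of the probable intent. It does not remove the problem, because Section 6.2.7 lists missing values separately from inability. A programmer following it would code every absent test as 0. Even within an attended visit, a component skipped for a practical reason would lose up to 4 of the 12 points.

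Four further objections limit the size of the point, and they stand.

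- The 80% completeness is stated for the co-primary and main secondary outcomes, and its shortfall includes deaths. Taking off 7 points for control mortality and 6 for transplantation (Section 9.11) leaves about 20 − 7 − 6 = 7 points. At a mean of 8 these would shift an arm mean by 0.07 × 8 = 0.56.
- The protocol projects no difference in missingness between arms. Section 5.3 names burn-out and modality change as possible risks of nocturnal dialysis. That makes a gap plausible but does not give its size.
- The LEP is also measured at month 4, which Section 6.1 places before significant attrition.
- The LEP is exploratory.

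A reader might infer that the rule leaves the LEP unable to support or challenge the PHC result, or that a false effect is to be expected. The documents support neither. The month-4 comparison is less exposed, and a false effect needs an imbalance that the plan does not forecast.

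**Conclusion.** The point holds as a conflict between Section 6.2.7 and Sections 5.1.5.2.1 and 9.9, and it should be corrected. Followed as written, Section 6.2.7 analyses non-functional absence as total loss of function. Equal missingness costs precision and dilutes a true effect in proportion to the missing share. Unequal missingness biases the comparison against the arm that loses more patients.

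The mechanism and direction follow from the rule itself. The size does not: 0.8 points (0.6 to 1.0) for a 10-percentage-point gap rests on an assumed mean of 8 (6 to 10). The simulated error rates and power losses rest on assumed means, SDs, baseline correlation and missing shares, with values missing completely at random. They are illustrations, not forecasts. No co-primary or main secondary result is affected.

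**What to change.** Reconcile Sections 5.1.5.2.1, 6.2.7 and 9.9 as follows.

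1. Score a component 0 only when the patient could not complete it, or it was not attempted, because of documented physical inability. Record a reason code. An attempt alone should not trigger a 0.
2. Treat every other absent value as missing under the model used for the LEP (Section 9.5, or Section 9.7 if it is analysed as ordinal), with the Section 9.9 sensitivity analyses.
3. Handle death and transplant as for the other secondary outcomes.

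The cost is one reason-code field, a few lines of wording, and more missing LEP values to report.

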# 6.2.8 Samples for Biorepositories

Additional biological samples will be obtained to be stored to use in future studies of hemodialysis patients. In particular,  $\beta_2$ -microglobulin and C-reactive protein will measured from samples obtained at baseline, 4 and 12 months. Patient consent will be obtained to specifically address the collection of these specimens. Among those participants who consent for storage of biological specimens, serum and plasma specimens will be shipped to the National Institute of Diabetes and

Digestive and Kidney Diseases Biosample Repository at Fisher BioServices at study baseline, months 4 and 12. During the course of the trial, all studies using the biorepository samples must receive the approval of the FHN Ancillary Studies Committee and follow the study policies of the trial regarding ancillary studies.

## 6.3 Definitions, Monitoring and Reporting of Patient Events

## 6.3.1 Outcome Classification Committee

An Outcome Classification Committee will be composed of the Clinical Center Principal Investigators, who will review all deaths and 100 hospitalizations to verify cause of death or hospitalization (see below). The members of the Outcome Committee will be trained by the Data Coordinating Center in order to provide a standard classification system for patient deaths and hospitalizations. The Data Coordinating Center will remove any information that can identify the randomization status of the patient being reviewed so that members of the Outcome Committee will be blinded to the patient's treatment allocation.

## 6.3.2 Hospitalizations

All hospitalizations will be categorized by the Clinical Center (Site) PIs by access versus non-access hospitalization and by primary and secondary reason for hospitalization using one of a number of hospitalization categories by system, coded with a modification of the HEMO Study code list.

The detailed hospitalization discharge form will be completed by the Site PI, Co-Investigator or Collaborator from the patient's Clinical Center and reviewed by the Consortium Center PI ([name]) or his designee. After each hospitalization that does not lead to a death, a subject will sign a release to allow the hospital to provide the details of the hospitalization to the FHN Clinical Center team. (In addition, each subject will sign a blanket release form annually, to make it easier for the Clinical Centers to obtain details on hospitalizations that lead to death and to obtain details on deaths.) The Clinical Center will contact the hospital involved. Data to be obtained and recorded on the detailed hospitalization discharge form include date of admission, date of discharge, whether the patient was in the intensive care unit during the hospital stay, whether a vascular access procedure was performed during the hospital stay, the primary and secondary reason for hospitalization as coded by the categories on the form, and the standard adverse event questions about the expectedness and relatedness of the hospitalization. The answers to these questions will be based on either the discharge summary associated with that hospitalization or a narrative description of the hospitalization provided by a physician who was responsible for the care of the patient. The FHN detailed hospitalization discharge form will also capture whether the Site PI, Co-Investigator's or Collaborator's categorization was based on an actual discharge summary or some other form of documentation, and this form should be submitted to the Data Coordinating Center within 30 days of the patient's hospital discharge.

For the first 12 FHN Nocturnal Study hospitalizations, the Outcome Committee will be available for consultation but will not do formal reviews. After the first 12 FHN Nocturnal Study hospitalizations have occurred, for the next 52 daily study hospitalizations, the Clinical Center will send a hospitalization packet including the hospitalization discharge form and a discharge summary/narrative description to the DCC. The DCC staff will send create a hospitalization packet including these data and send this packet to one blinded member of the Outcome Committee, and he will complete Outcome Committee Hospitalization Review Form reassessing whether it was a CV or Access hospitalization. (The precise "reason for hospitalization" code associated with the hospitalization is not reassessed.) If the CV and access determination coded by the Outcome

Committee member and the Clinical Center PI, Co-Investigator or Collaborator differ, then the case will be adjudicated by the Outcome Committee during the monthly conference call until resolution can be reached. The final categorization with respect to CV and Access will be recorded in the "final categorization" section at the end of the Outcome Committee Hospitalization Review Form. The hospitalization code chosen by the committee as the "final categorization" will be used for subsequent analyses of these 52 hospitalizations.

The agreement of the Outcome Committee and Clinical Center classifications of the initial 52 hospitalizations will be evaluated as part of the Vanguard assessment of the trial. Subsequently, 12 hospitalizations per year (one hospital admission form per calendar month) will be selected for review by a member of the Outcome Committee and adjudication by the Outcome Review Committee if necessary.

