### 6.3.3 Deaths

The death form will be completed by the Principal Investigator from the involved Clinical Center, who will classify the death using a modification of the HEMO Study coding system. This system will allow for the classification of deaths by organ system, such as cardiac and infection-related. A death packet with the death form and specific patient information will be sent by the Clinical Center to the Data Coordinating Center, who in turn will forward this data to members of the Outcome Committee. For hospitalizations resulting in death, the same information as described above for hospitalizations will be obtained. If the death did not occur in the hospital, then the principal investigator will provide a narrative describing the circumstances of the patient's death and the presumed cause of death based on the patient's history and events leading up to the patient death. One member of the Outcome Committee will review this information and verify the cause of death on the death form. If the death coded by the Outcome Committee member and the Clinical Center PI differ, then the case will be discussed by the Outcome Committee during the monthly conference call. The death code chosen by the committee will be used for subsequent analysis.

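### The hospitalization reviewer is sent the site's own coded form, so the 52-case agreement is not based on independent codings and tends upward by an unknown amount

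*Protocol*

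**What the plan says.** The site investigator completes a discharge form after each hospitalization. Among other items it records "the primary and secondary reason for hospitalization as coded by the categories on the form" (Protocol 6.3.2). The first 12 stays get no formal committee review. For the next 52, "the Clinical Center will send a hospitalization packet including the hospitalization discharge form and a discharge summary/narrative description to the DCC". The DCC is then to "send this packet to one blinded member of the Outcome Committee", who records CV and access status on a separate review form. The precise reason code is not reassessed.

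Section 6.3.1 gives the meaning of blinding: "The Data Coordinating Center will remove any information that can identify the randomization status of the patient being reviewed". No sentence removes or withholds the site's coding.

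Escalation depends on disagreement. If the determinations of the "Committee member and the Clinical Center PI, Co-Investigator or Collaborator differ, then the case will be adjudicated by the Outcome Committee". The section then states: "The agreement of the Outcome Committee and Clinical Center classifications of the initial 52 hospitalizations will be evaluated as part of the Vanguard assessment". After that, 12 stays a year are reviewed, one per calendar month.

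Deaths (6.3.3) follow the same pattern. The packet holds the site's completed death form, and "One member of the Outcome Committee will review this information and verify the cause of death on the death form". All deaths stay under review. On membership, 6.3.1 says: "An Outcome Classification Committee will be composed of the Clinical Center Principal Investigators".

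**The concern.** The trial is unblinded, so the site that labels a stay as access or non-access, CV or not, knows the patient's arm. The committee's second look is the safeguard against labels colored by that knowledge, and the 52-case agreement is the planned evidence on whether site labels can be relied on.

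A reviewer who sees the site's answer before giving an opinion is anchored to it. This has two consequences. A case in which the reviewer defers never reaches the full committee, because a difference is the only trigger. The agreement statistic also counts that deference as concordance, so it cannot separate reliable site coding from reviewers going along with it.

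The labels matter for the rate of non-access hospitalization or death (analyzed in 9.6) and for the access and CV hospitalization rates in 5.1.5.5. Section 5.1.3.5 also expects the spread of outpatient access repair to make access hospitalizations harder to identify. It defines a non-access stay only as an overnight acute-care stay, so the access label rests on judgment.

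**Working it through.** The protocol states no agreement figure, kappa or threshold, so there is nothing to reproduce. The check is a trace of what the reviewer receives, followed by an illustration and a count of events.

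**Trace**

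1. The site codes the reasons on the discharge form (6.3.2).
2. That form, with the summary or narrative, goes to the DCC (6.3.2).
3. The DCC builds a packet including these data and sends it to one member (6.3.2).
4. The only stated redaction is of treatment allocation (6.3.1).
5. The member reassesses CV and access status with the site's codes in view. A difference from the site is the only route to adjudication (6.3.2).
6. Agreement is computed on these 52 reviews (6.3.2).

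So "blind" here means blind to arm, not to the site's answer, and step 6 does not use independent codings.

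**Illustration (both inputs are assumptions)**

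Let a be the agreement an independent reviewer would reach. Let q be the share of would-be disagreements in which the reviewer adopts the visible code.

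Observed agreement = a + (1 − a)q. Inflation = (1 − a)q. Discordant cases among 52 = 52(1 − a)(1 − q).

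| a | q = 0 | q = 0.25 | q = 0.50 | q = 0.75 |
|---|---|---|---|---|
| 0.70 | 0.700 (15.6 discordant) | 0.775 (11.7) | 0.850 (7.8) | 0.925 (3.9) |
| 0.80 | 0.800 (10.4) | 0.850 (7.8) | 0.900 (5.2) | 0.950 (2.6) |
| 0.90 | 0.900 (5.2) | 0.925 (3.9) | 0.950 (2.6) | 0.975 (1.3) |

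The inflation runs from 0.10 × 0.25 = 2.5 points to 0.30 × 0.75 = 22.5 points. It is zero if q = 0 and positive for any q above zero. The direction follows from the design; the size does not follow from anything in the protocol.

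**How many events the review covers**

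Section 9.11 gives 1.19 non-access stays per year in the reference trial and projects control-group rates 40% lower: 1.19 × 0.6 = 0.714 per patient-year. Applying this to both arms:

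- With no losses: 0.714 × 90 = about 64 stays.
- With 7%/yr death and 6%/yr transplantation: patient-years = 90 × (1 − e^−0.13)/0.13 = about 84.4, giving 0.714 × 84.4 = about 60 stays.

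The first 12 unreviewed stays plus the 52 reviewed make 64. Those 64 include access stays, for which the protocol gives no rate, so exact coverage is unknown. The 52-case block is nevertheless large relative to the expected events. Section 6.3.2 calls these 52 daily-study stays although the 12 before them are the Nocturnal Study's; I take them as this trial's.

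**The case against.** The best defense is that this is a verification step and is described as one. Section 6.3.1 speaks of verifying cause, and 6.3.2 says the precise code is not reassessed. The reviewer also has the discharge summary or narrative, the same kind of source the site coded from. Every discharge form is in addition reviewed by the Consortium Center PI or a designee. This stands as far as it goes: the reviewer has source material, and the protocol does not promise blind double coding. It does not rescue the agreement figure, which is informative about site coding only if the second coding is made without sight of the first.

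A reader might infer more than the protocol supports:

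- **That inflated agreement unlocks the drop to 12 reviews a year.** That schedule is set in advance, with no threshold or condition.
- **That site labels pass largely untested.** With 52 reviews against about 60 expected non-access stays, and the Consortium Center PI's look at every form, that is too strong.
- **That each lost dispute alters 1/60, or 1.7%, of non-access events.** A dispute may concern CV status only, might be settled in the site's favor, and may involve an access stay, which is outside the 60.
- **That the co-primary results are at risk.** The composites in 9.3 use death from any cause and survival time. Cause of death does not enter them, and the agreement check and step-down concern hospitalizations only.
- **That the patient's own PI will review the packet.** The committee consists of site PIs and no routing rule is written. But the requirement of one blinded member, and a process that presumes reviewer and site can differ, already point away from it. The rule needs stating, but the text does not show a breach.

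**Conclusion.** The point holds in a limited form. Because the reviewer sees the site's coded form, the 52-case agreement is not measured on independent codings, and deference would both suppress adjudication and bias that agreement upward. The protocol does not allow the size to be estimated. The 2.5 to 22.5 points above rest on assumed independent agreement of 70 to 90% and assumed deference of 25 to 75%.

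The reach is the access/non-access and CV labels in the secondary hospitalization outcomes. The non-access rate is itself given inconsistent status: Table 7 and one of the two versions of the opening text in 9.4 list it as a main secondary outcome, while 5.1.3.5 says it is not one and is underpowered. This is a low-cost improvement to a stated procedure and does not threaten the trial's main conclusion.

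**What to change.** In 6.3.2, have the DCC mask the site's reason codes and any access/CV categorization before the packet goes out. The member codes CV and access status first, from the discharge summary or narrative alone. Compute the 52-case agreement on those codings, and send differences to the committee as now. For consistency, mask the site's cause-of-death code in 6.3.3 in the same way.

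Add one sentence sending each packet to a member from a center other than the patient's, so that the existing requirement of a blinded member is met in practice.

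The cost is slightly more redaction and routing work at the DCC, which already strips allocation information from these packets. No new data or reviewers are needed. More cases may reach the monthly call, which is the purpose of the change.
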